 - HIV or AIDS based on self-report.
 - Steroid use with the exception of over-the-counter topical and nasal steroids such as Flonase.
 - Allergy medication or regular antihistamine use.

- Seizure disorders. Acceptable if managed with medication and free of seizure activity for 5 years.
 - Smoking or the use of nicotine replacement products in the past 6 months.
 - Use of dietary supplements containing vitamins (except Calcium and Vitamin D), minerals, herbal or plant-based preparations, fish oil or homeopathic remedies during study participation unless willing to discontinue prior to enrollment.
 - Current participation in another research study.
 - Non-English speaking.
 - No social security number.
 - Participation in another research study.
- **Withdrawal/Termination Criteria:** Low compliance including taking less than 80% of study supplements, or missing study visits. Subjects who manifest an allergic reaction to the study supplement or placebo. Negative health effects as determined by the study physician. In the event of a withdrawal/termination, study subjects will be asked to discontinue their study supplement, and, if necessary due to negative health effects, will be referred to their primary care physician.

*Note: Screening lab values that would interfere with study outcomes are determined at the discretion of the study physician.

D. Risk/Benefit Assessment: We do not anticipate any major risks or hazards to participants in this study.

There are no benefits to participation in this study. EMIQ has been independently evaluated by an expert panel as safe and has been categorized as GRAS (generally recognized as safe) according to the Food and Drug Administration (FDA)(see attachment “5. FDA GRAS EMIQ”). Other investigators have conducted similar clinical studies with EMIQ at doses comparable to those in this study and reported no adverse effect.

While all measures to ensure confidentiality will be taken, it is an ever present possibility that it may be lost. Stored samples will be labeled with a unique number (code) that will not contain any private information such as name or date of birth to ensure the samples cannot be identified. There is no intention for allowing anyone other than the principal investigator to have access to these codes. If [name] turns this study over to a new principal investigator, he will give the key code to the new principal investigator.

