Participants and nursing staff will be able to reach the study physician, [name], or a covering physician 24 hours/day. Specific participant complaints will be addressed on an individual basis and appropriate referrals to primary care providers or other health care providers will be made. Participants' health status will be assessed weekly through phone or email and will be updated by the members of the study team. While there is no evidence to suggest so, there might be some adverse effects from EMIQ's effect on fat loss, or EMIQ itself. If these problems are reported by participants, the condition will be assessed to determine if these adverse events are potentially study-related. Further, in the case of these and any other adverse event, the study physician will advise participants on the appropriate assistance or action to take, and then counseled to seek further appropriate assistance.

Compensation will not be available for any research-related injury, and treatment may incur charges for the subject. The Nursing staff at the MRU is basic BLS (CPR) certified and trained in the use of an automatic external defibrillator (AED). In all emergency situations, the MRU Nursing staff will provide immediate basic life support (BLS) response, call 911 and continue to provide emergency supportive care as needed (e.g., monitoring, oxygen, airway maintenance) until emergency medical service (EMS) arrives. Their philosophy is to provide early access to the most appropriate and advanced care for treatment of study subjects. Treatment by the MRU Nursing staff and/or the staff physician is provided at no cost to the participants. All additional treatment including the cost of an ambulance is charged to the study subject. There are no funds available for these costs to be paid by the HNRCA or by study funds. This information is provided to participants prior to their signing an informed consent form.

A participant may be dropped from the study should a reported adverse reaction to the study supplement be considered severe.

G. Subject Safety and Data and Safety Monitoring Plan

Classification and Reporting of Adverse Events and Unanticipated Problems for This Study

An **Unanticipated Problem** is defined as: An incident, experience, or outcome that meets all of the following criteria:

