1. The nature, severity, or frequency is unexpected for the subject population or research activities as described in the current IRB approved protocol, supporting documents, and the ICF(s).
2. It is related or possibly related to participation in the research.
3. It suggests the research may place the subject or others at a greater risk of harm than was previously recognized.

An **Adverse Event (AE)** is defined as: Any untoward or unfavorable medical occurrence in a human subject, including any abnormal physical exam or laboratory finding, symptom, or disease, temporally associated with a subject’s participation in the research.

AEs are classified by three categories:

1. Severity: *Non-serious* or *Serious*
2. Relation to Participation in Research: *Related, Possibly Related, or Unrelated*

The classification of the potential relationship to the intervention will be determined based on the following scheme:

Definite	Temporal pattern and known or expected adverse event response pattern, confirmed by stopping the intervention and reappearance of adverse event on re-challenge.
Probable	Temporal pattern and known or expected adverse event response pattern, confirmed by stopping the intervention and which could not be explained by the participant’s clinical state.
Possible	Temporal pattern and known or expected adverse event response pattern, confirmed by stopping the intervention and which could have been produced by a number of other factors.
Unknown	Relationship for which no evaluation can be made.
Not Related	Adverse event for which sufficient information exists to indicate that the cause is unrelated to the study intervention.

3. Expectation: *Expected* or *Unexpected* (determination is based on the known risks associated with the study supplement and procedures, natural progression of an underlying illness, and health characteristics of the study population)
4. Location: *Internal* (occurring at the HNRCA) or *External* (occurring at a site that is not under the jurisdiction of the Tufts MC/TUHS IRB)

Further, a **Serious Adverse Event (SAE)** is an **AE** that meets the following criteria:

1. Results in death, or
2. Is life-threatening, or
3. Results in hospitalization or prolongation of existing hospitalization, or
4. Results in a persistent or significant disability/incapacitation, or
5. Results in congenital anomaly/birth defect, or

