6. May jeopardize the subject's health and may require medical or surgical intervention to prevent one of the other outcomes listed above.

AEs are Unanticipated Problems only when they meet all three criteria in the definition of an unanticipated problem.

In the event of an Unanticipated Problem, or adverse event, staff will immediately notify the PI and study physician. Once notified, the PI, [name], will take immediate action to eliminate or minimize risk to enrolled subjects. The study physician, [name], will assess the severity of the unanticipated problem, and determine its relation to the study protocol. Each unanticipated problem will be reported, with all supporting documentation, according to the following IRB guidelines within 5 business days:

Information that does not fall under any of the categories does not require reporting to the IRB.

1. Harm experienced by a subject or other individual, which in the opinion of the investigator is **unexpected** and **related/possibly related** to the research procedures.
 - A. A harm is "**unexpected**" when its specificity and/or severity is **inconsistent** with risk information previously reviewed and approved by the IRB in terms of nature, severity, frequency, and characteristics of the study population.
 - B. A harm "**possibly related**" when there is a reasonable likelihood that the incident, experience, or outcome may have been caused by the procedures involved in the research.
- b. Information that indicates a new or increased risk, or a new safety issue. For example:
 - A. New information (e.g., an interim analysis, safety monitoring report, publication in the literature, sponsor report, or investigator finding) indicates an increase in the frequency or magnitude of a previously known risk, or

uncovers a new risk or greater risk of harm (including physical, psychological, economic, or social harm) than was previously known or recognized.

- B. An investigator brochure, package insert, or device labeling is revised to indicate an increase in the frequency or magnitude of a previously known risk, or describe a new risk
- C. Withdrawal, restriction, or modification of a marketed approval of a drug, device, or biologic used in a research protocol
- D. Complaint of a subject that indicates subjects or others might be at increased risk of harm or at risk of a new harm

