## Statistical Analysis Plan

All subjects who completed the study were included in the analysis. Summary statistics were expressed in mean  $\pm$  S.D. for continuous variables, and counts (percentage %) for categorical variables. Differences between treatment groups were tested using Student's *t*-test. Two-sample Wilcoxon test is used when variables appear to violate distributional assumptions. Model assumptions were assessed within an ANCOVA model predicting 12 week outcome, adjusting for baseline. Fisher's exact test or chi-square test was performed for categorical variables. An  $\alpha$  level of  $p < 0.05$  was considered statistically significant. Statistical analysis was conducted in R 3.4 (R Core Team 2017, Vienna Austria).

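### The adverse-event item called Severity records seriousness, and no defined scale for intensity exists, although the protocol relies on the words severe and severity elsewhere

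*Protocol*

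**What the plan says.** Protocol Section III.G, under the classification and reporting of adverse events, introduces its scheme with "AEs are classified by three categories" and then lists four items: severity, relation to the research, expectation and location. The severity item is "Severity: *Non-serious* or *Serious". The same section defines a serious event by six outcome criteria, of which one is "Results in hospitalization or prolongation of existing hospitalization, or".

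Four other places in the protocol depend on severity:

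- Section III.F, Volunteer Consent and Safety: "A participant may be dropped from the study should a reported adverse reaction to the study supplement be considered severe".
- Section III.G, first criterion for an unanticipated problem: "The nature, severity, or frequency is unexpected for the subject population or research activities".
- Section III.G, IRB reporting guidelines: a harm counts as unexpected partly by comparing its severity with the risk information already reviewed.
- Section III.G: the study physician "will assess the severity of the unanticipated problem, and determine its relation to the study protocol".

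The SAP names no AE variable. Its only relevant provision is general: "Fisher's exact test or chi-square test was performed for categorical variables". It analyses participants who completed the study.

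**The concern.** Seriousness and severity are different attributes. Seriousness is about consequence and drives reporting; severity is about how intense the event was. The protocol puts the label of the second on the values of the first and has no item for the second.

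Two things are at stake. First, AE records kept to this scheme cannot show whether events on EMIQ were more intense than events on placebo. Serious events are probably uncommon in participants selected by a long list of medical exclusions, so most AEs may share one code. Second, a removal because a reaction was judged severe, or a finding that a harm was more severe than expected, would rest on a term that the classification does not define. Different staff could apply it differently.

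**Working it through.** No sample size, rate or power figure underlies this point, so the check is a comparison of the texts.

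**Step 1: what the item can record.** It has two values, Non-serious and Serious. Neither is an intensity grade and neither is *severe*.

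**Step 2: what Serious means.** The six criteria are death; threat to life; new or prolonged hospitalization; lasting or significant disability; birth defect; and jeopardy to health that may need intervention to prevent one of these. All concern consequences. The sixth is the broadest and will catch some intense events, but only those that threaten one of the listed outcomes.

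**Step 3: whether another item records intensity.** Relation, expectation and location do not. A reading of both documents for mild/moderate/severe grades, numeric grades or named toxicity criteria finds none.

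**Step 4: a test case.** Take several days of intense nausea with no hospital contact and no threat of a listed outcome, and one brief, trivial episode of nausea. Both are Non-serious. If they share relation, expectation and location, the scheme gives them identical codes.

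**Step 5: the four uses of the term, set against the item.**

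| Use | What it needs | What the item gives |
|---|---|---|
| Possible removal (III.F) | Whether a reaction is severe | Whether it is serious |
| Unanticipated problem, criterion 1 (III.G) | Severity compared with expectation | Two outcome-based levels |
| Unexpected harm (III.G) | Severity compared with reviewed risk information | Two outcome-based levels |
| Study physician's assessment (III.G) | A severity judgement, for unanticipated problems only | No intensity grade |

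The word also occurs in the clause on device effects, which has no bearing on a capsule study.

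**Step 6: who would be in a by-arm table.** Section III.B plans 64 enrolled so that 50 complete, which allows for 64 − 50 = 14 non-completers. A participant dropped for a reaction is one of these and falls outside the SAP's analysis set. A table limited to completers would omit the people to whom the term *severe* matters most.

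**Illustration only.** If the risk of a serious event were *p* per participant over the study, independently, the chance that nobody has one is (1 − *p*)^n. The documents give no value for *p*.

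| Assumed *p* | n = 50 completers | n = 64 enrolled |
|---|---|---|
| 0.5% | 0.995^50 = 78% | 0.995^64 = 73% |
| 1% | 0.99^50 = 61% | 0.99^64 = 53% |
| 2% | 0.98^50 = 36% | 0.98^64 = 27% |

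When nobody has a serious event, the item takes one value throughout. The result depends heavily on *p*, and the point does not rest on it: a serious/non-serious item cannot grade intensity at any rate.

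**The case against.** **Severe may simply mean serious.** Section III.G labels the item severity, so the physician's assessment, in the same section, can be read as choosing between its two values. On that reading only the word *severe* in Section III.F is loose. This is a possible reading, but the text never equates the terms, and the outcome criteria do not support equating them. It would also mean that a harm far more intense than expected, yet still non-serious, could not count as unexpected on severity.

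**Intensity is never captured.** A reader might infer this, and it goes too far. The AE form is not among the documents, narrative notes may describe intensity, and the physician does assess the severity of unanticipated problems. What the documents support is narrower: no defined scale, and a physician assessment that covers only a subset of events and has no grades.

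**Removals cannot be checked, or participants are unprotected.** The documents do not support this either. The rule in Section III.F is discretionary, and the withdrawal criteria in Section III.C separately list "Negative health effects as determined by the study physician". Under the monitoring plan the principal investigator reviews reasons for drop-out, discusses AEs weekly with the study physician and gives the IRB summaries of all AEs.

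**Aim 2 fails.** It does not. Hypothesis 2 is to be judged on heart, liver and kidney function and psychological state. Laboratory values and depression scores carry their own magnitude, and no AE-intensity endpoint is planned.

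**The remedy is preference.** Renaming the item and clarifying one word would settle the wording. That is correct as far as it goes, but it would leave the severity tests in Section III.G with nothing to refer to.

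**Conclusion.** The point holds as a conflation of two concepts in a stated classification rule. The item named Severity has two values, none of them an intensity grade, and four other provisions use a term that it does not measure.

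The consequence is moderate: a weaker descriptive comparison of AEs between arms, and inconsistent use of *severe* and *severity*. The primary efficacy analysis and the stated safety measures are untouched. The conclusion assumes that the AE form follows the protocol's scheme. If the form already carries a defined intensity grade, only the protocol wording needs correction. No numerical size is claimed, since the probabilities above rest on assumed rates and do not measure how many events would differ in intensity. The change is worth making because it is cheap and improves the safety data.

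**What to change.** 1. In Section III.G, rename the first item *Seriousness (Serious / Non-serious)*.
2. Add a separate item, *Severity (mild / moderate / severe)*, with a short definition of each level, rated for every AE.
3. Reconcile the passages in Sections III.F and III.G so that *severe* and *severity* refer to the new item. Whether and when a participant is removed stays with the sponsor.
4. In the SAP, add a descriptive table of AEs by arm and worst intensity per participant, covering everyone who received study capsules (EMIQ or placebo), including those dropped.
5. In the same edit, correct the count of classification items, which is announced as three but listed as four.

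The cost is one extra rating per AE and one table. With about 25 completers per arm the table should be read as description, not as a test.

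### Definite, Probable and Possible all require a known or expected pattern confirmed by stopping, so a new EMIQ effect can only be graded Unknown, a grade with no place on the protocol's three-level scale

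*Protocol*

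**What the plan says.** Section III.G of the protocol (Subject Safety and Data and Safety Monitoring Plan) contains three texts on relatedness.

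- **The three-level scale.** In the list of adverse-event classifications, relation to participation is recorded as "Related, Possibly Related, or Unrelated".
- **The five-grade table under it.** It is introduced as binding: "The classification of the potential relationship to the intervention will be determined based on the following scheme". The entry for Definite is "Temporal pattern and known or expected adverse event response pattern, confirmed by stopping the intervention and reappearance of adverse event on re-challenge". The entry for Probable begins "Temporal pattern and known or expected adverse event response pattern, confirmed by stopping the intervention and which could not be explained by the"; its closing words rule out an explanation from the subject's own condition. The entry for Possible begins "Temporal pattern and known or expected adverse event response pattern, confirmed by stopping the intervention and which could have been produced"; its closing words allow that several other causes may be responsible. The other two grades are Unknown, for when no evaluation is possible, and Not Related, which needs enough information to attribute the event to another cause.
- **The IRB reporting guidelines.** A harm is possibly related "when there is a reasonable likelihood that the incident, experience, or outcome may have been caused by the procedures involved in the research". This definition mentions neither a known pattern nor stopping.

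Two other items in III.G matter. An Unanticipated Problem must be unexpected in nature, severity or frequency, must be related or possibly related, and must suggest greater risk than was recognised. Expectation is also a separate classification item, apart from relation.

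On what is already known, section III.D says that similar studies at comparable doses were done "and reported no adverse effect".

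**The concern.** A causality scale for a safety aim should be able to register an effect that nobody has seen before. Here the two conditions that such an effect is least likely to meet, a pattern already known or expected and confirmation by stopping, are built into every positive grade, including the weakest. By the protocol's own account there is little prior EMIQ experience of harm to match against.

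Two things are at stake. First, the relatedness grade of a new event becomes a product of the definitions and not of the physician's assessment. Second, an assessor who carries the table's grade into the Unanticipated Problem test could conclude that a non-serious, novel event fails the relatedness criterion. An assessor who uses the reporting definition could conclude the opposite for the same event. There is no DSMB, so consistent grading depends on the study physician and the principal investigator.

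**Working it through.** There is no figure to reproduce. The check sets the conditions of each grade side by side and runs typical events through them.

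| Grade | Temporal pattern | Known or expected | Confirmed by stopping | Further condition |
|---|---|---|---|---|
| Definite | required | required | required | returns on re-challenge |
| Probable | required | required | required | not explained by clinical state |
| Possible | required | required | required | other factors could explain it |
| Unknown | – | – | – | cannot be evaluated |
| Not Related | – | – | – | information points to another cause |

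**Event A: a new effect that resolves when capsules are stopped.** It fails the second condition, so 0 of 3 positive grades are open. Not Related does not fit either, because nothing points to another cause. Unknown is what remains, although the physician may in fact be able to evaluate the event.

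**Event B: an event in a subject who continued the supplement.** It fails the third condition, so again 0 of 3 are open, whether or not the pattern is known. Without information pointing elsewhere, it is Unknown.

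**Event C: an allergic reaction that resolves on stopping.** The withdrawal criteria in III.C foresee allergic reaction, so the pattern can be called expected. Probable or Possible is available. The scheme can therefore produce positive grades, but only for foreseen events.

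**Mapping.** Five grades must be reduced to three levels. Definite, Probable, Possible and Not Related have natural places, though none is stated. Unknown has none, and it is the grade that receives events A and B.

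**Against the Unanticipated Problem definition.** Take an event that is unexpected in nature. If relatedness is read from the table, criterion 2 (at least possibly related) requires a known or expected pattern, while criterion 1 is met because the event is unexpected. The two cannot hold together. An event of a known kind that is unexpected only in severity or frequency could still satisfy both, so the conflict is confined to new kinds of event.

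**Against the reporting definition.** Event A can have a reasonable likelihood of being caused by the research and so be possibly related for reporting, while the table denies it the grade Possible. Nothing in III.G says which text prevails.

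**The case against.** The strongest reply is that the consequences are small. Much of this stands.

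- A reader might infer that the adverse-event table will support Hypothesis 2 by construction. The documents do not support that. Neither plans an adverse-event table by relatedness. Section I rests Hypothesis 2 on heart, liver and kidney function and psychological state, and the SAP compares groups without mentioning causality grades. A difference between arms on those measures would show whatever grade was given.
- A reader might infer that a new event would be kept from the IRB, particularly from the sentence "Information that does not fall under any of the categories does not require reporting to the IRB". That is also too strong. The reporting guidelines use their own definition of possibly related and the investigator's opinion. They add a category for new or increased risk that has no relatedness test. The Data and Safety Monitoring Plan has all serious adverse events reported whatever their relation, and summaries of all adverse events given to the IRB.
- A reader might infer that a new effect would be graded Not Related. That grade needs positive information about another cause.
- A reader might infer that everything first seen at visit 5 must fail the stopping condition. Supplementation ends at 12 weeks, and the notes to the blood collection scheme have abnormal safety laboratory values repeated, which can show the course after stopping. Other visit 5 findings, such as the Beck Depression Inventory, have no planned repeat.
- A reader might infer that no EMIQ event can match a known pattern. Event C shows otherwise, and expected is wider than previously reported.

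A lenient reader could also take the pattern condition to mean any recognisable response pattern. The text does not say so, and on that reading the stopping condition would still exclude event B.

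What the reply does not remove is the contradiction. The table is stated to determine the classification, and nothing subordinates it to the reporting definition.

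**Conclusion.** The table is wrong as written and should be amended. For a new effect, or an event without a stop of supplement, 0 of 3 positive grades are available and Unknown is the residual. This follows from the definitions and does not depend on the true event rate. The table contradicts the Unanticipated Problem definition for events unexpected in nature, contradicts the reporting definition of possibly related, and does not map to the three-level scale.

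The effect is confined to relatedness grading and to whether a non-serious new event is classed as an Unanticipated Problem. Adverse-event counts by arm, the Aim 2 comparisons and the reporting of serious events are not affected. The conclusion assumes that the table is applied literally, as its introductory sentence says. A physician who grades by ordinary judgement would avoid the problem, but only by departing from the protocol.

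**What to change.** Reconcile the three texts in III.G into one scale, used for both grading and reporting:

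1. Define Possible by the reporting guidelines' existing test, a reasonable likelihood that the event may have been caused by the research. Remove the pattern and stopping conditions from that grade. The existing test refers to research procedures, so state that the supplement is included.
2. Leave expectedness to the separate Expectation item, so that it is not also a condition of being possibly related.
3. State how the five grades map to the three levels. Where Unknown goes is for the sponsor to decide. Placing it with Possibly Related is the cautious choice, at the price of more reportable events.

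This opens Possible to a new effect. Definite and Probable would keep their present conditions unless the sponsor revises them too.

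The cost is one table edit by amendment, and somewhat more events will be listed as possibly related. The SAP is written in the past tense, so grading may already be complete. In that case, report all adverse events by arm regardless of relatedness and disclose the scheme that was used.
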